5.4 Safety Follow-Up

All patients will have safety follow-up after permanent discontinuation of study drug (enzalutamide). Safety follow-up should occur approximately 30 days after the last dose of study drug or before initiation of cytotoxic chemotherapy, a lutamide (bicalutamide, nilutamide, or flutamide), or a new investigational therapy, whichever occurs first. In the event that one of these treatments is initiated before safety follow-up occurs (eg, a physician not associated with protocol MDV3100-18 initiates the treatment, and study site personnel are not aware of the treatment until afterward), safety follow-up should be scheduled as soon as possible.

If treatment is discontinued due to an adverse event or serious adverse event, the event(s) must be followed up as described in [Section 8.3.6](#). For patients who refuse further clinic study visits, telephone contact should be attempted and documented to review for adverse events through approximately 30 days after the last dose of study drug or before initiation of cytotoxic chemotherapy, a lutamide (bicalutamide, nilutamide, or flutamide), or a new investigational therapy, whichever occurs first. There is no long-term follow-up phase.

Safety follow-up procedures are listed in [Table 8](#).

Table 8: Safety Follow-Up Procedures

Activity / Assessment	Comment
General Activities	
Complete physical examination	Measure vital signs (temperature, blood pressure, heart rate) and weight. ECOG performance status (Table 13). Assess systems per standard of care at the study site.
Adverse events review	Record any new or ongoing adverse events.
Concomitant medications review	Record any new medications or changes in ongoing medications.
Study drug accountability	Collect all remaining study drug and record study drug returned.
Local Laboratory Evaluations	
Serum chemistry, hematology	Refer to analytes listed in Table 12.
PSA	

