8.3.2.1 Adverse Event Reporting Periods

Collection and reporting of adverse event information will begin at the time the patient signs informed consent for serious adverse events and from the first dose of study drug for nonserious adverse events, and will continue through 30 days after the last dose of study drug treatment or before initiation of cytotoxic chemotherapy, a lutamide (bicalutamide, nilutamide, or flutamide), or a new investigational therapy, whichever occurs first. Additional reporting instructions for serious adverse events and events of special interest are provided in [Section 8.3.5](#).

All adverse events from the time of the first dose of any study drug treatment must be documented on the adverse event case report form and in the patient's clinical record. Any event occurring during screening must be documented on the medical history case report form and in the patient's clinical record for any patient who subsequently meets eligibility criteria and proceeds to treatment.

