Appendix 2: Study Schedule of Activities

Study Period Study Week Study Days Window (Days) [3]	Screening	Treatment					Unsched [1]	Safety FUP [2]
	-4 to -1	1	5	13	21 then q8w	Varies	Varies	Varies
	-28 to -1	1	29	85	141 then q56d	na	na	na
	na	na	±3	±3	±7	na	na	na
General Activities								
Informed consent, study ID number [4]	X							
Medical history	X							
Eligibility criteria incl. BPI, ECOG	X							
12-lead electrocardiogram (local read)	X							
^{99m} Tc-MDP bone scintigraphy	X [5]					X [6]		
CT or MRI of chest/abdomen/pelvis	X [5]					X [6]		
Complete physical examination [7]	X	X [8]						X
Brief physical examination [9]			X	X	X [10]		X	
Adverse events review [11]	X	X	X	X	X		X	X
Concomitant medications review	X	X	X	X	X		X	X
Enzalutamide dispensing		X		X	X			
Study drug accountability			X	X	X			X
Enrollment authorization form [12]	X							
Local Lab Evaluations								
Hematology, serum chemistry	X	X [8]	X	X	X [10]		X	X
Testosterone	X							
Prostate-specific antigen	X	X		X [13]	X	X		X
Central Lab/Imaging Evaluations [14]								
Circulating tumor cells		X [15]				X [16]		
¹⁸ F-NaF PET/CT imaging		X (F-1) [17]		X (F-2)		X (F-3) [18]		

[1] Any time necessary to assess or follow up adverse events, at the patient's request, or per investigator decision.

[2] Approximately 30 days after the last dose of study drug (permanent discontinuation) or before initiation of cytotoxic chemotherapy, a lutamide (bicalutamide, nilutamide, or flutamide), or a new investigational therapy, whichever occurs first.

[3] Drug supply must be taken into account when scheduling visits during windows. Visit procedures may be split across the window to allow for drug resupply and completion of study procedures.

- [4] Must be before any study-specific procedures. May obtain before the screening window. Ensure consent is on the current version of the form.
- [5] Must be within 28 days before day 1. Send copy of bone scintigraphy image to the central imaging vendor for archiving.

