3.5. Safety Endpoints

Safety endpoints will be summarized based on the on-treatment period unless otherwise specified.

On-treatment is defined as the period between the first dose of the study drug to the earliest of 30 days after the last dose of study drug treatment, the start of cytotoxic chemotherapy, the start of a lutamide (bicalutamide, nilutamide, or flutamide), or the start of a new investigational therapy. Adverse events occurring on the same day as the first dose of study treatment will be considered to have occurred during the on-treatment period. All other assessments which occur on the same day as the first dose of study treatment will be considered.

[figure not shown]
Safety data collected outside the on-treatment period as described above will be listed but not summarized.

An adverse event is considered treatment emergent relative to a given treatment if:

- the event occurs for the first time during the on-treatment period and was not seen prior to the start of treatment, or
- the event was seen prior to the start of treatment but increased in severity during the on-treatment period.

Adverse events will be coded to preferred term and system organ class using the Medical Dictionary for Regulatory Activities (MedDRA) and classified by severity using the CTCAE, version 4.

Hematology and chemistry results will be programmatically graded according to the NCI CTCAE version 4 for relevant parameters. Parameters which cannot be graded will be summarized relative to the normal range (ie, normal range high or normal range low). Additional details are provided in Section 6.6.

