6.6.4. Laboratory Data

Laboratory data in this study consist of hematology values and chemistry tests. Only data collected from the central laboratory during the treatment-emergent period will be summarized. Laboratory data collected outside the treatment-emergent period will only be listed in the data listings.

Laboratory results will be converted to International System of Units (SI) units which will be used for applying toxicity grades and for all summaries.

Quantitative data will be summarized using simple descriptive statistics (mean, standard deviation, median, quartiles, minimum, and maximum) of actual values and change from baseline for each nominal visit over time (ie, unscheduled assessments will be excluded). The total number of patients for change from baseline will include all patients in the treatment arm who have both a baseline and a value at the nominal visit.

As described in Section 3.4, baseline will defined as the last assessment performed on or prior to date of the first dose of study treatment. If there are multiple assessments that meet the baseline definition on the same day without the ability to determine which was truly last, then the worst grade will be assigned as the baseline grade.

Results collected as strict inequalities (eg, >10, <10) will be converted to numeric values by subtracting a factor of <0.001>. Expressions of the form" \geq " or " \leq " will be converted to the end point. These numeric values will be evaluated for clinically significant abnormalities, but will not be included in calculations of summary statistics.

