6.6.7. ECOG

[figure not shown]
Descriptive summaries at baseline and at the safety follow-up will be provided. These include:

• Number and percentage of patients for each of the six categories.

The ECOG performance status scores will be listed.

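### The laboratory summary window closes exactly 30 days after the last dose, but the only scheduled post-treatment blood sample is due at about day 30, so a sample from day 31 on misses the worst-grade, shift and liver tables

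*SAP*

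**What the plan says.** **The analysis window.** SAP 3.5 sets the default: "Safety endpoints will be summarized based on the on-treatment period unless otherwise specified". The period runs from first dose to "the earliest of 30 days after the last dose of study drug treatment" or the start of chemotherapy, a lutamide or a new investigational therapy. For anything later, "Safety data collected outside the on-treatment period as described above will be listed but not summarized".

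**Laboratory data.** SAP 6.6.4 restates the rule: "Laboratory data collected outside the treatment-emergent period will only be listed in the data listings". The CTCAE worst-grade shift table, the normal-range shift table (lowest and highest result) and the liver table (ALT, AST or total bilirubin above 5 x ULN) are each limited to the treatment-emergent period.

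**The visit.** Protocol 5.4 says: "Safety follow-up should occur approximately 30 days after the last dose of study drug", or before one of the listed new therapies if that comes first. Protocol Table 8 puts serum chemistry and hematology at this visit. The window row of Appendix 2 reads not applicable for it.

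**Related text.** Adverse event collection under protocol 8.3.2.1 "will continue through 30 days after the last dose of study drug treatment", unless a listed therapy starts first. Protocol 10.4 defines the treatment-emergent period with the same 30-day end. For performance status, SAP 6.6.7 names the visit itself: "Descriptive summaries at baseline and at the safety follow-up will be provided".

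**The concern.** A sharp cut-off has been placed on the nominal day of a visit whose timing is only approximate. A sample on day 30 counts. The same sample on day 31 does not, although it comes from a visit the protocol schedules. No rule in the SAP assigns a follow-up sample after day 30 to any summary.

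The sample can matter because routine testing is sparse late in the study. After week 21, chemistry and hematology are scheduled only every 16 weeks (protocol Table 5 and Appendix 2, note 10). For a man who stops treatment shortly before his next scheduled draw, the follow-up sample can be the only scheduled result covering up to about 16 weeks of dosing. The patients exposed to the cut are those who have discontinued, and with about 20 patients one man is 1/20 = 5 percentage points in a safety table.

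**Working it through.** The plan gives no figure to reproduce here. The check is of text and dates, followed by an illustration of size.

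**1. Window against visit**

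- Window end: last dose + 30 days, no tolerance (SAP 3.5, 6.6.4; same period in protocol 10.4).
- Visit: about 30 days after last dose, no window (protocol 5.4, Appendix 2).
- The opening for exceptions in SAP 3.5 does not help laboratory data, because SAP 6.6.4 repeats the exclusion and each of the three tables names the treatment-emergent period.
- SAP 2.2 describes safety follow-up as lasting to day 30 at most, which does not match the protocol's approximate timing.

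A scheduled sample on day 31 or later is therefore listed only.

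**2. Direction of the effect**

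Let G be a patient's worst grade among samples inside the window and g the grade of the late sample. The plan reports G. With the late sample included, the table would report max(G, g), which is never less than G. So the number of patients at or above any grade can only fall or stay the same when the sample is dropped. The same holds for the number with a low or high value and for the number above 5 x ULN. Nothing changes for a patient unless the late sample is his worst value.

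**3. Share of visits after day 30**

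The documents give no distribution of visit days. Assume, for illustration only, that visits are uniform over the whole days 30 − w to 30 + w. The share after day 30 is w / (2w + 1). The values w = 3 and w = 7 are borrowed from the treatment-period visits in protocol 5.2.1 and are not stated for this visit.

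| w | Share after day 30 | Expected of 20 patients |
|---|---|---|
| 0 | 0 | 0 |
| 3 | 3/7 = 42.9% | 8.6 |
| 7 | 7/15 = 46.7% | 9.3 |

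The last column also assumes that all 20 have a follow-up visit and that no listed new therapy has closed the window first. These are shares of samples excluded. The number of table entries that change will be smaller, by step 2.

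**4. Against the protocol's laboratory plan**

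The 30-day period is the protocol's own. However, the sentences on shift tables in protocol 10.4 compare baseline with post-baseline grade without restating a period limit, and the synopsis plans shifts from baseline to each later visit, as appropriate. The safety follow-up is a later visit.

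**The case against.** **The period is the protocol's own convention.** This stands. A reader might infer that the SAP shortened the period; protocol 10.4 shows that it did not. What remains is that the period does not fit the timing of the visit meant to close it.

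**Nothing forces the visit past day 30.** This also stands. Because adverse events are collected through day 30, a reader might infer that sites must wait until then, and that most samples are lost (if all visits fell evenly on days 30 to 37, the share would be 7/8 = 88%). The documents do not say so. Protocol 5.4 pulls the visit earlier when a listed therapy is about to start and allows telephone review for patients who refuse clinic visits. The 88% figure assumes the late timing it would need to prove.

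**A man stopping for toxicity will often have other samples.** Largely true. Protocol 5.2.7 allows unscheduled chemistry and hematology, SAP 5.2.4 uses unscheduled results in worst-case on-treatment derivations, and the laboratory stopping criteria in protocol 5.3 themselves require a measured value. Clinically significant abnormalities with onset by day 30 are also recorded as adverse events. The protection is incomplete, since protocol 8.4 keeps results from a different laboratory used for unscheduled or urgent care out of the database.

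**Vital signs.** A reader might extend the point to them. SAP 6.6.5 plans no worst-grade, shift or liver table for vital signs, only values and changes at scheduled time points, and the default in SAP 3.5 yields to more specific text. Whether a late follow-up reading is summarized is unclear; its exclusion is not established.

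**Conclusion.** The point holds for laboratory data. As written, a scheduled follow-up sample drawn on day 31 or later is left out of the worst-grade shift, normal-range shift and liver tables, and the omission acts in one direction. Its size cannot be known from the documents: 0% of follow-up samples if every visit falls by day 30, and about 43% to 47% under an assumed even spread of ±3 or ±7 days. The effect on the counts is smaller than the share of samples dropped. Late results are still listed, so nothing is lost from the record.

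The documents do not support a claim that the safety tables are materially biased, that most follow-up samples are excluded, or that vital signs are dropped. This is a gap in a descriptive single-arm study that is worth closing because closing it is cheap.

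A separate and larger problem sits in the same section. SAP 6.6.4 summarizes only central-laboratory data, while protocol 8.4 and section 12 have all safety tests done locally. Read literally, these tables would be empty whatever the window.

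**What to change.** - **SAP 3.5 and 6.6.4:** state that laboratory results from the scheduled safety follow-up visit, identified by visit label and drawn before any new chemotherapy, lutamide or investigational therapy, are included in the worst post-baseline, shift and liver tables and are shown on their own safety follow-up row. The label should take precedence over the day-based windows of SAP Appendix 3.
- **Adverse events:** keep the 30-day limit for onset.
- **SAP 6.6.5:** state that the safety follow-up visit is a scheduled time point for vital signs.
- **SAP 2.2:** reconcile its day-30 end of safety follow-up with the approximate timing in protocol 5.4.
- **SAP 6.6.4:** correct the central-laboratory wording. The tables need this in order to contain data.

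A visit-label rule is better than moving the cut-off to day 37. The ±7-day window in protocol 5.2.1 belongs to treatment-period visits, and Appendix 2 gives none for this one.

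The cost of the laboratory change is one sentence and one programming condition. The downside is that a few results drawn shortly after day 30 off drug enter the worst-case tables. Samples taken after a listed new therapy has started stay excluded.

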4. ANALYSIS SETS

While the protocol notes an intent-to-treat population, the below As Treated population will be used instead since the study is single-arm and exploratory in nature. Certain restrictions will later be noted where baseline and certain post-baseline measurements are required for particular endpoints.

4.1. As Treated (AT)

The As Treated (AT) population is defined as all enrolled patients who receive any amount of study treatment.

5. GENERAL METHODOLOGY AND CONVENTIONS

There is no planned interim analysis. The final analysis will occur when all patients have progressed or have otherwise been followed for two year or are no longer being followed due to withdrawal of consent, lost to follow-up, or death. Since the study is phase 2 and exploratory, no adjustments for multiplicity will be made.

5.1. Hypotheses and Decision Rules

The primary purpose of this study is to assess the NaF imaging as a method for evaluating treatment response in bone lesions at the time of progression. The sample size of 20 patients was chosen for practical clinical considerations.

Due to the exploratory nature of this study, there is no formal hypothesis. Instead, estimation will be the primary aim.

5.2. General Methods

Confidence intervals will be done with 95% coverage. No adjustments to the confidence intervals are planned for any multiple testing.

5.2.1. Pooling of Data by Study Site

[figure not shown]
In order to provide overall estimates, data will be pooled across study sites. Furthermore, the small number of enrolled patients makes an analysis by study site not feasible. However, study site will be used as a factor in the ANCOVA models so as to improve precision of the estimates.

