2.2. Study Design

This is a phase 2, open-label, single-arm trial of enzalutamide in adult male patients who are chemotherapy-naïve, and who have bone-metastatic castration-resistant prostate cancer.

In this study approximately 20 adult male patients will be enrolled across 3 sites in the United States. Eligible patients must have bone metastatic disease in at least 2 lesions with a PSA \geq 2 ng/mL. Patients must not have received any prior chemotherapy previously.

Following screening, enrolled patients will have baseline 18F-NaF PET/CT imaging (NaF-1) and then begin open-label treatment with enzalutamide. PSA response will be determined at week 13 when a second 18F-NaF PET/CT imaging (NaF-2) is obtained. Patients with any increase in PSA at week 13 may discontinue treatment and proceed to safety follow-up unless the investigator considers continuation of study drug to be beneficial. For all continuing patients, PSA will be monitored every 8 weeks after week 13 and other study assessments will continue to be obtained. A third 18F-NaF PET/CT imaging (NaF-3) and a follow-up 99mTc-MDP bone scintigraphy will be performed when PSA progression (an increase of at least 25% AND an absolute increase of at least 2.0 ng/mL above nadir), radiographic progression (bone or soft tissue), or other clinically relevant progression (eg, significant bone pain or a skeletal-related event) is observed, or at 2 years without progression after initiation of treatment. No 99mTc-MDP bone scintigraphy will be required at the time the NaF-3 bone scan is obtained if bone disease progression was confirmed earlier on bone scintigraphy obtained at investigator discretion.

Total study duration will be approximately 36 months.

[figure not shown]
Enzalutamide will be administered one daily at a starting dose of 160mg/day. Dose modifications downwards are possible to either 120 or 80 mg/day, per protocol section 6.2.4.

Study periods include screening, treatment, and safety follow-up. Safety follow-up applies to patients who are off protocol therapy and continues to the earliest of 1) 30 days after last dose, 2) death, 3) lost to follow-up, 4) withdrawal of consent, or 5) enrollment into another anti-cancer clinical trial.

The study schematic is provided in Figure 1.

Figure 1. Study Schematic

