5.2.8. Analysis of Covariance

A linear model for analysis of covariance (ANCOVA) will be used to analyze continuous data collected at baseline and at particular post-baseline visits. The dependent variable in the ANCOVA model will be the change from baseline at the specified post-baseline windowed visit. The model will include fixed effects terms for:

- Treatment (as a categorical variable);
- Baseline value (as a continuous variable);
- Study site (as a categorical variable).

The observed margins option (OM) will be implemented in assigning categorical weights when calculating the least squares means. There will be no imputation for missing data in the analyses. While there is only one treatment arm in this study, the inclusion of the fixed effect for treatment is needed in order to produce the desired least squares mean.

The model-adjusted mean change from baseline will be presented at the specified postbaseline visit using the least squares mean, its standard error, and its 95% confidence interval.

In the event of convergence problems, then the fixed effect term for study site will be removed and the model re-run.

Sample SAS code for the ANCOVA model is found in Appendix 2. Sample SAS Code.

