6. ANALYSES AND SUMMARIES

All efficacy analyses will be based on the AT population. Any confidence intervals presented will be 2-sided 95% CI. No adjustments to the confidence intervals are planned for any multiple testing. The start day for time to event analyses will begin at the date of first study drug.

Safety analyses (adverse events, laboratory tests, etc.) will be based on the AT population.

A grid-summary of the efficacy analyses can be found in Appendix 4. Summary of Efficacy Analyses.

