Appendix 2. Sample SAS Code

Sample SAS code follows below. The code is meant for a general start. Further dialogue between the programmer and statistician is encouraged.

KM quartiles and plot

```
proc lifetest data=x1 alpha=0.05 conftype=loglog plot=s;
time months*eventn(0);
run;
```

The variable "months" is a continuous variable representing months of exposure. The variable "eventn" is a binary variable (0=censor, 1=event).

Hazard ratio

```
proc phreg data=x1;
model months*eventn(0) = group / rl alpha=0.05;
run;
```

[figure not shown]
The variable "months" is a continuous variable representing months of exposure. The variable "eventn" is a binary variable (0=censor, 1=event). The variable "group" is a binary variable for median cutpoint (below/above the median change from baseline).

Clopper-Pearson Confidence Interval

```
proc sort data=y1 out=y2;
by descending response;
proc freq data=y2 order=data;
tables response / binomial(exact) alpha=0.05;
run;
```

The descending sort is included to ensure that the response modeled is 1 and not 0. The input dataset y1 has a one-record-per-patient format similar to:

| PATIENT | RESPONSE |
|---------|----------|
| 1001 | 0 |
| 1002 | 1 |
| 1003 | 0 |
| ••• | ••• |
| ••• | ••• |

[figure not shown]

ANCOVA Analysis

```
proc mixed data=z1;
class treat studysite;
model efchg = treat efbase studysite;
lsmeans treat / cl alpha=0.05 om;
run;
```

The variables "efchg" and "efbase" represent change from baseline and baseline values respectively. The OM option is used when the categorical term "studysite" is used in the model. If "studysite" is not included for convergence reasons, then the OM option can be removed.

While there is only one treatment arm in this study, the inclusion of the fixed effect for "treat" is needed in order to produce the desired least squares mean.

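### With one arm, the ANCOVA LS mean is the raw mean change, so adjustment cannot sharpen the estimate, and its 95% CI under-covers the population mean change when baseline predicts change

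*SAP*

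**What the plan says.** The SAP describes a single-arm study in which "approximately 20 adult male patients will be enrolled across 3 sites in the United States". SAP 5.1 states that "there is no formal hypothesis. Instead, estimation will be the primary aim", and SAP 5.2 adds that "Confidence intervals will be done with 95% coverage".

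For continuous data at baseline and follow-up, SAP 5.2.8 models the change on treatment (one level), the baseline value and study site, without imputation. Site is dropped only if the model fails to converge. "The model-adjusted mean change from baseline will be presented at the specified postbaseline visit using the least squares mean", together with its standard error and 95% CI. Appendix 2 codes the request as "lsmeans treat / cl alpha=0.05 om". SAP 5.2.9 applies the same model to log-transformed data and back-transforms the result to a percent change.

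SAP 5.2.1 gives the reason for the site term: "study site will be used as a factor in the ANCOVA models so as to improve precision of the estimates". No reason is given for the baseline term. The SAP does not say whether the LS mean is meant to estimate the mean change in the patient population or the mean at the baselines and site mix that happened to be enrolled.

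**The concern.** In a randomised comparison, adjusting for baseline corrects chance imbalance between arms and can reduce the true variance of the treatment difference. Here there is no second arm. Averaging the fitted model back over the same patients returns the average of their changes, so there is nothing to correct. The model's standard error still falls if baseline explains part of the change. A shorter interval around an unchanged estimate looks like a gain in precision, but for the population mean it is a variance component left out.

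This matters because the study aims at estimation, so the interval is the main statement of uncertainty. It also matters because baseline is likely to predict change: change is computed from baseline, which ties the two together.

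**Working it through.** **Inputs.** From the SAP: about 20 patients, 3 sites, one arm, two-sided 95% intervals, and the model in 5.2.8 and Appendix 2. Four parameters are estimated (intercept/treatment, baseline, two site contrasts), so the residual df are 20 − 4 = 16. The documents give no SD, baseline–change correlation or site split, so those values below are assumptions.

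**Step 1: the estimate.** Least squares with an intercept passes through the means. Let L be the column means of the design matrix X (mean baseline, observed site shares). Then L′β̂ = ȳ, the raw mean change, and SE = √(MSE × L′(X′X)⁻¹L) = √(MSE/n). A numerical check with site splits 8/7/5, 14/4/2 and 10/9/1 gave differences from ȳ below 10⁻¹⁵. The identity needs the covariate mean and site weights to come from the patients analysed. If patients with only a baseline value enter those means, the LS mean can differ from ȳ. On the log scale the same identity gives the raw mean log-ratio.

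**Step 2: the width.** The model interval has half-width t₁₆√(MSE/n); the one-sample interval has t₁₉·s/√n. The quantile ratio is 2.120/2.093 = 1.013. The model interval is therefore shorter only if MSE/s² < (2.093/2.120)² = 0.975, that is, if baseline and site explain more than about 2.5% of the variance after the df correction. When they truly explain nothing, it averaged 1% wider in simulation and was shorter in 36% of trials.

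**Step 3: coverage of the population mean change.** Let baseline explain a share R² of the variance σ² of change, with normal data. The true variance of ȳ is σ²/n, but the model SE² estimates σ²(1 − R²)/n. Hence

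coverage = P(|T₁₆| < 2.120 × √(1 − R²)).

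| R² (assumed) | 2.120 × √(1 − R²) | Coverage | Average-width ratio to one-sample t: 1.013 × √(1 − R²) |
|---|---|---|---|
| 0% | 2.120 | 95.0% | 1.01 |
| 9% | 2.022 | 94.0% | 0.97 |
| 25% | 1.836 | 91.5% | 0.88 |
| 49% | 1.514 | 85.0% | 0.72 |

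Simulation with site in the model gave 94.1%, 91.2% and 85.4% for the last three rows. In a separate set of 8,000 trials per scenario at n = 20, the one-sample t interval covered the population mean 94.7–95.4% of the time. At n = 15 the model interval covered 91.3% with 25% explained and 85.0% with 50%.

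**Step 4: is that range plausible?** With equal variances at both visits and between-visit correlation ρ, the correlation of change with baseline is −√((1 − ρ)/2). This is −0.32 at ρ = 0.8, −0.50 at ρ = 0.5 and −0.71 at ρ = 0, so R² is 10%, 25% and 50%. The shortfall depends on R², not on the sign of the correlation.

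**Step 5: other targets and the site term.**
- Mean conditional on the observed baselines and site mix: the model interval covered 94.9–95.3% in every n = 20 scenario, and the one-sample interval over-covered by up to five points.
- Site as the only predictor, site mix fixed: the model interval covered 95.0–95.1% and the one-sample interval 96.2–97.7%.
- Site as the only predictor, site mix random: the model interval covered 94.2% and 92.0% with 10% and 25% explained.

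**The case against.** The strongest reply is that the interval is correct for one legitimate target. For the mean at these baselines and this site mix, coverage is nominal. The three sites are part of the design, so treating them as fixed is reasonable, and removing between-site variance is then valid. The sentence in 5.2.1 speaks only of site, whereas the larger loss comes from the baseline term in 5.2.8, which carries no precision claim. All of this stands, and it places the main defect in 5.2.8.

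It is also true that the study is exploratory, that no decision rule rests on these intervals, and that the size of the shortfall depends on assumed values. The 85% figure requires baseline to explain about half the variance of change.

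The reply does not settle the matter. The SAP never states the conditional target, and a mean change with a 95% CI in a study aimed at estimation will naturally be read as describing the population.

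A reader might go further and infer that every change-from-baseline interval in the study is too short. Step 2 shows otherwise: with little explained, the interval is slightly wider. A reader might also infer that the main results are affected. They are not: SAP 6.1 uses a Clopper-Pearson interval for the primary endpoint, and SAP 6.2 uses summary statistics and histograms for the secondary.

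**Conclusion.** The concern holds in a conditional form. Given covariate means and site weights from the analysed patients, the adjusted mean is the unadjusted mean, so the ANCOVA cannot estimate the population mean change more precisely. Where baseline predicts change, its 95% CI under-covers that mean: by about one point if baseline explains 9% of the variance, about three and a half points at 25% and about ten points at 49%. These figures assume n = 20, roughly normal data, and shares of explained variance that the documents do not supply.

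It would be too strong to call the site rationale simply false. With the site mix taken as fixed, the shorter interval from a site-only adjustment has its nominal coverage.

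The impact is confined to the LS-mean change analyses under SAP 5.2.8 and 5.2.9. Their endpoints are redacted, so the effect on any particular result cannot be seen. It is worth correcting because the remedy is cheap and the stated 95% coverage is otherwise not secured for the natural target.

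**What to change.** - **SAP 5.2.8 and 5.2.9:** state that the target is the population mean change. Report the mean change, or the back-transformed mean log-ratio, with the one-sample t 95% CI.
- **Alternative:** keep the LS mean but add covariate variation to its standard error. With the site mix taken as fixed, SE² = MSE/n + b²·s²_baseline/n, where b is the fitted baseline slope and s²_baseline is the baseline variance (within site, if baselines differ between sites). A random site mix needs a further term.
- **If the ANCOVA is retained:** use it to describe the baseline slope, or label its mean as conditional on the observed baselines and site mix.
- **SAP 5.2.1:** reword so that the site factor is not said to give a more precise estimate of the population mean.
- **Appendix 2:** align the sample code, and confirm that margins are taken from the patients analysed.

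The cost is SAP wording and, for the t interval, simpler code. Intervals become somewhat wider when baseline predicts change: the one-sample interval is about 1/0.88 = 1.14 times as wide as the model interval at 25% explained. For a purely conditional target, the one-sample interval is conservative.
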